**Starting dose for the SAD**

A single dose of 50 mg appears to be an appropriate starting dose for the single ascending dose SAD study for the following reasons:

- The proposed 33-fold safety margin to the human equivalent dose (HED) derived from the no-observed-adverse-effect level (NOAEL, 100 mg/kg) in the 28-day dog toxicology study is based on twice daily dosing (50 mg/kg BID) compared to once daily dosing proposed in humans. The daily dosing frequency was changed from QD to BID in the animal studies to increase tolerability of TBI-223 when orally administered to dogs.
- The more relevant NOAEL at 50 mg/kg QD (HED 27 mg/kg) in the repeat-dose 28-day dog toxicology study provides a 17-fold safety margin to a first-in-human (FIH) starting dose of 100 mg QD. However, in the nonclinical safety pharmacology cardiovascular study in dogs, a trend of increasing QTc prolongation was observed in dogs after a single oral administration of TBI-223 at 50 and 100 mg/kg (max increase 11 to 14 msec from baseline, 12 msec from control 2 hours post-dose) at 1 to 13 hours post-dose, and a statistically significant increase in QTc interval was detected at 200 mg/kg (mean increase 22 msec from baseline and control 2 to 5 hours post-dose, and 21 to 25 hours post-dose).
- Significant toxicity was observed in the 28-day dog toxicology study at a dose of 200 mg/kg/day (100 mg/kg BID) including intermittent and continuous tremors, ataxia, convulsions in several animals, QTc prolongation (10 to 11% baseline), decreased body weight, and vomitus. It should be noted that the dosing interval between twice daily dosing was not provided, and the clinical observations were

- performed at 1 and 12 hours post-dose, and not 2 to 4 hours at  $C_{max}/T_{max}$  when tremors may have a greatest chance of occurring and being detected.
- In the 14-day dog toxicology study with orally administered TBI-223, dose reduction from 200 mg/kg daily to 150 mg/kg (75 mg/kg BID) on Day 7 continued to cause tremors on Days 8 to 10 of dosing. This may be a result of drug accumulation noted with repeated dosing with TBI-223. Cage-side observations more appropriately timed at 3 to 4 hours post-dose and 6 to 9 hours post-dose in this 14-day study may have provided a greater opportunity of detecting tremors in animals. Had the clinical observations been performed at similar times in the 28-day dog toxicology study, perhaps tremors might have been observed at 100 mg/kg/day (50 mg/kg BID), reportedly the NOAEL in this study. No tremors were observed at 75 mg/kg/day QD in dogs in the 14-day study.

In the first cohort of this Phase 1 study, the proposed starting dose of 50 mg once daily (QD) is 66-fold lower than the HED of 3243 mg/day, derived from the lowest NOAEL, which was 50 mg/kg BID (100 mg/kg/day) in a 28-day dog GLP toxicity study. The proposed starting dose is 17-fold less than the HED of a single 50 mg/kg dose in dogs.

The predicted  $C_{max}$  and  $AUC_{0-24hr}$  at the proposed first in human dose of 50 mg once daily are 0.711  $\mu$ g/mL and 2.5  $\mu$ g.hr/mL, which are 20.4- and 86-fold less than the NOAEL in the dog toxicity study, respectively. The proposed starting doses for this first-in-human SAD study are well below the predicted NOAEL. The following dose escalations for each cohort receiving a single dose are proposed: 50 mg, 100 mg, 300 mg, 600 mg, 1200 mg, and 2000 mg. These proposed doses (cohorts) could change (e.g. if bioavailability is lower than expected or for potential emerging safety reasons).

For all the reasons noted above, a starting dose of 50 mg in the SAD would likely provide a reasonable margin of safety to any adverse -cardiovascular or CNS- effects observed with TBI-223 during administration to dogs.

Dose escalation will be guided by emerging safety and pharmacokinetic data so that predicted median  $C_{max}$  of a cohort can exceed 20.2  $\mu$ g/mL (the NOAEL plasma  $C_{max}$  in the 28-day GLP dog toxicity study) only if, after data review, the prior dose was considered safe and well tolerated. Human plasma M2 metabolite exposure will be measured at each dose level, and the M2 exposure for next dose level will be predicted for safety analysis by comparing to M2 exposures in dogs. However, the planned doses could change if the generated bioavailability is lower than expected. Therefore, additional cohorts may be enrolled if deemed appropriate by the Sponsor to repeat a dose level or to study other dose levels or a different dosage formulation. These decisions regarding planned additional cohorts will not take place until the Sponsor, in conjunction with the Principal Investigator and dose-escalating committee, has

determined that adequate safety, tolerability, and pharmacokinetics from the previous cohort have been demonstrated to permit proceeding to the next cohort. The Institutional Review Board (IRB) should be immediately notified of this revised approach for review and approval. The new approved dose for Cohort 6 will be 2000 mg.

## **2 OBJECTIVE**

The primary objective of the study is:

- To evaluate the safety and tolerability of single doses of TBI-223 oral suspension, TBI-223 oral enteric capsules, and TBI-223 tablet formulations in healthy adult subjects.

The secondary objectives of the study are:

- To determine the pharmacokinetics of TBI-223 and its metabolite M2 after single doses of TBI-223 oral suspension, TBI-223 oral enteric capsules, and TBI-223 tablet formulations in healthy adult subjects; and
- To compare the rate and extent of absorption of a single dose of TBI-223 oral suspension, TBI-223 oral enteric capsules, and TBI-223 tablet formulations when administered in healthy adult subjects either after a high-calorie, high-fat meal or in the fasting state.

## **3 STUDY DESIGN SUMMARY**

### **Part 1:**

Up to 48 subjects in 6 dosing cohorts are planned to be enrolled; within each cohort, 6 subjects will be assigned to active treatment and 2 to placebo.

Each subject will participate in 1 dose level. Based on interim pharmacokinetic data obtained during the dose escalation, a dose cohort will be selected to return for additional dosing after a high-calorie, high-fat meal (food-effect cohort).

Each cohort will be dosed in 2 groups in order to monitor subjects for adverse experiences, in particular, convulsions (in the dog toxicity studies, tremors were observed at  $C_{max}$  or plasma concentration of  $\geq 82\mu\text{g/mL}$ , and convulsions were observed at plasma concentration or  $C_{max}$  of  $\geq 158\mu\text{g/mL}$ ).

In the first cohort, a sentinel group of 3 subjects (2 active and 1 placebo) will be dosed at least 24 hours before the remaining 5 subjects (4 active and 1 placebo).

The remaining cohorts will be dosed in 2 groups of 4 subjects each (3 active and 1 placebo), at least 24 hours apart.

Safety will be assessed throughout the study for all subjects. Safety assessments will include physical and neurological examinations, vital signs, ECGs, cardiac monitoring, AEs, and clinical laboratory tests (including hematology, serum chemistry, coagulation, and urinalysis).

Blood and urine will be collected for clinical laboratory evaluations.

Female subjects will have blood collected for serum pregnancy testing. Postmenopausal females will have blood collected to measure follicle-stimulating hormone (FSH) levels.

[figure not shown]
Blood will be collected for pharmacokinetic analysis.

Dose escalation to the next cohort (i.e., dose level) will not take place until the Sponsor, in conjunction with the Principal Investigator, has determined that adequate safety, tolerability and pharmacokinetic data from the previous cohorts have been demonstrated to permit proceeding to the next cohort.

The Principal Investigator, in conjunction with the Sponsor may collect additional blood if necessary, for repeat laboratory or safety evaluations including AE follow up.

An overview of the dosing groups in Part 1 is presented in Figure 1.

**Figure 1 Dosing Groups**

Based on the interim pharmacokinetics for the dose escalation decisions, 10 subjects will be selected to participate in the **food-effect cohort**. These subjects will receive TBI-223 or placebo under fasting conditions in the first study period. They will return after a washout of at least 7 days or 5 half-lives (whichever is longer) of their fasting dose to receive the same dose under fed conditions.

Additional cohorts (8 subjects per cohort) may be enrolled if it is deemed appropriate by the Sponsor to repeat a dose level or to study another dose level or dosage formulation. The IRB will be notified of this revised approach.

Note: In the event that a dose level is repeated to study a different dosage formulation, procedures and analyses will be conducted as outlined in Appendix 5.

Interim pharmacokinetic analyses will be performed for the dose escalation decisions, to select the dose for the food-effect cohort, and to reconsider the timing, reducing, or adding of sampling time points as the study progresses.

Blood samples will be obtained prior to study drug administration on Day 1 and at serial timepoints through 72 hours after study drug administration. Plasma pharmacokinetic samples will be analyzed for TBI-223 and M2 using validated analytical methods. Appropriate pharmacokinetic parameters will be calculated for each formulation using non-compartmental methods.

An unblinded pharmacist will be responsible for dispensing the study treatment and to ensure that study personnel are blinded.

Except for during the fed period of the food-effect cohort, TBI-223 or matching placebo dose will be administered orally with 200 mL of water after a minimum 10-hour overnight fasting, and food will be given approximately 4 hours after each dose level.

Table 2 presents the actual dose cohorts for Part 1 of the study.

**Table 2 Actual Dose Cohorts for Part 1**

Cohort a (Group b )	Dose c
1 (sentinel group)	Single dose of 50 mg TBI-223 (n=2)
1 (remainder of cohort)	Single dose of 50 mg TBI-223 (n=4)
2 (Group 1)	Single dose of 100 mg TBI-223 (n=3)
2 (Group 2)	Single dose of 100 mg TBI-223 (n=3)
3a (Group 1)	Single dose of 300 mg TBI-223 (n=3)
3a (Group 2)	Single dose of 300 mg TBI-223 (n=3)
3b (Capsule cohort)	Single dose of 300 mg (TBI-223 in oral enteric capsules) (n=4)
4 (Group 1)	Single dose of 600 mg TBI-223 (n=3)
4 (Group 2)	Single dose of 600 mg TBI-223 (n=3)
5 (Group 1)	Single dose of 1200 mg TBI-223 (n=3)
5 (Group 2)	Single dose of 1200 mg TBI-223 (n=3)
6 (Group 1)	Single dose of 2000 mg TBI-223 (n=3)
6 (Group 2)	Single dose of 2000 mg TBI-223 (n=3)
7 (Group 1)	Single dose of 2600 mg TBI-223 (n=3)
7 (Group 2)	Single dose of 2600 mg TBI-223 (n=3)

mg = milligram; n = number of subjects.

- a) Additional cohorts may be enrolled if deemed appropriate by the Sponsor to repeat a dose level or to study another dose level or another dosage formulation.
- b) Dosing between Groups 1 and 2 to occur at least 24 hours apart.
- c) Subjects will be dosed under fasted conditions. One of the dose cohorts will be selected to return for an additional dose under fed conditions.

## Part 2:

Cohort 8: A minimum of 24 subjects in 4 dosing arms are planned to be enrolled; within each arm, 6 subjects will be assigned to receive a single dose treatment. Subjects will be assigned to one of the following arms and dose:

- Arm 1 – TBI-223 SR Tablets (Prototype 1) - 1800 mg dose (3 x 600 mg tablets), under fed conditions
- Arm 2 – TBI-223 SR Tablets (Prototype 2) - 1800 mg dose (3 x 600 mg tablets), under fed conditions
- Arm 3 – TBI-223 SR Tablets (Prototype 3) - 1800 mg dose (2 x 900 mg tablets), under fed conditions
- Arm 4 – TBI-223 IR Tablets - 2000 mg dose (2 x 1000 mg tablets), under fasting conditions

Procedures and analyses will be conducted as outlined in Appendix 6.

Cohort 9: The 6 subjects from Cohort 8, Arm 4, who received the IR tablet formulation fasted will return after a 7-day washout and receive a single dose of TBI-223 IR Tablets, 2000 mg dose (2 x 1000 mg tablets), under fed conditions.

If more than 2 subjects of these 6 subjects from Cohort 8 drop-out, they will be replaced by healthy volunteers (a minimum of 4 subjects are needed to complete Cohort 9).

Procedures and analyses will be conducted as outlined in Appendix 6.

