#### **6.4 Confinement**

Part 1 fasting cohorts, and Part 2, Cohort 8, Arm 4 only: Subjects will be admitted to the research center on Day -2 (Part 1) or Day -1 (Part 2) and remain confined until after completion of the 48-hour procedures on Day 3. Subjects will return for a follow-up visit approximately 72 hours after dosing (Day 4) and receive a follow up phone call on Day 11 (+1 day).

Part 1 food-effect cohort, Part 2, Cohort 8, Arms 1-3 and Cohort 9: Subjects will be admitted to the research center on Day -2 of Period 1 and Period 2 (Part 1) or Day -1 (Part 2) and remain confined until after completion of the 48-hour procedures on Day 3 of each study period. Subjects will return for a follow-up visit approximately 72 hours after dosing (Day 4) in each study period. Subjects will receive a follow up phone call on Day 11 (+1 day) of Period 2.

Please note that Cohort 9 is the same 6 subjects that were in Cohort 8, Arm 4 (IR tablet formulation) under fed conditions. In Cohort 8, Arm 4, subjects fasted.

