## **APPENDIX 5 REPEAT COHORT USING DIFFERENT DOSAGE FORMULATION**

Procedures and analyses as outlined in this protocol will be the same, with the following exceptions:

- The dose of TBI-223 will be delivered in enteric capsules.
- All subjects will receive active treatment.
- A minimum of 6 subjects is needed. Ideally, all 8 subjects who participated in the original cohort will participate in the re-dose cohort. If less than 6 subjects from the original cohort agree to participate, additional subjects will be screened as needed in order to dose a minimum of 6 subjects.
- Repeat subjects will be assigned a new subject number so as not to break the blinding of the original cohort.
- The repeat cohort will not be blinded (blinding is not necessary because all subjects will receive the same treatment).
- Cardiac telemetry and Holter recording will not be performed during the re-dose cohort.
- Subjects will check-in on Day -1 instead of Day -2. With the exception of cardiac telemetry and Holter monitoring, the procedures that were previously scheduled for Day -2 will be performed on Day -1. The Day -1 results will be used to qualify repeat subjects for study participation. If additional subjects are needed, they will undergo screening to qualify for the study.
- Neurological examinations will be performed at Screening, Day -1, and at 3 and 48 hours postdose.

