## APPENDIX 6 PART 2 OF THE STUDY

Procedures and analyses as outlined in this protocol will be the same, with the following exceptions:

The dose of TBI-223 will be delivered as follows in Cohort 8:

- Arm 1 – TBI-223 SR Tablets (Prototype 1) - 1800 mg dose (3 x 600 mg tablets), under fed conditions
- Arm 2 – TBI-223 SR Tablets (Prototype 2) - 1800 mg dose (3 x 600 mg tablets), under fed conditions
- Arm 3 – TBI-223 SR Tablets (Prototype 3) - 1800 mg dose (2 x 900 mg tablets), under fed conditions
- Arm 4 – TBI-223 IR Tablets - 2000 mg dose (2 x 1000 mg tablets), under fasting conditions

In Cohort 9, the subjects from Cohort 8, Arm 4, who received the IR tablet formulation will be brought back following a 7-day washout and administered TBI-223 IR tablets, 2000 mg dose (2 x 1000 mg tablets), under fed conditions.

- A minimum of 6 subjects per treatment arm in Part 2.
- Part 2 will not be blinded (blinding is not necessary because all subjects will receive the same treatment).
- Cardiac telemetry and Holter recording will not be performed during Part 2. Subjects will check-in on Day -1 instead of Day -2. With the exception of cardiac telemetry and Holter monitoring, the procedures that were previously scheduled for Day -2 will be performed on Day -1. The Day -1 results will be used to qualify repeat subjects for study participation. If additional subjects are needed, they will undergo screening to qualify for the study.
- Neurological examinations will be performed at Screening, Day -1, and at 3 and 48 hours postdose.

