1 INTRODUCTION

This document details the planned statistical analyses for the Global Alliance for TB Drug Development, protocol “TBI-223-CL-001” study titled “A Phase 1, Partially-Blinded, Placebo-Controlled, Randomized Single Ascending Dose (SAD) with a Food Effect Cohort Study to Evaluate the Safety, Tolerability, and Pharmacokinetics of TBI-223 in Healthy Adult Participants”. The proposed analyses are based on the contents of protocol version 3.0, dated 21-Jan-2020 and Protocol Clarification Letter No. 4, dated 24-Feb-2020.

This is a partially blinded, placebo-controlled, randomized, SAD study with a food effect cohort. The study will be conducted at one study center in the United States.

Part 1

Part 1 of the study will have up to 6 planned dose levels. Based on interim pharmacokinetic data obtained during the dose escalation, a dose cohort will be selected to return for additional dosing after a high-calorie, high-fat meal (food-effect cohort).

Part 2

Part 2 of the study will comprise 4 arms each consisting of 6 subjects. Subjects will be assigned to one of the following dosing arms:

Arm 1	TBI-223 SR Tablets (Prototype 1) - 1800 mg dose (3 x 600 mg tablets) under fed conditions
Arm 2	TBI-223 SR Tablets (Prototype 2) - 1800 mg dose (3 x 600 mg tablets) under fed conditions
Arm 3	TBI-223 SR Tablets (Prototype 3) - 1800 mg dose (2 x 900 mg tablets) under fed conditions
Arm 4	TBI-223 IR Tablets - 2000 mg dose (2 x 1000 mg tablets) under fasting conditions

*IR = Immediate Release; SR = Sustained Release

The 6 subjects from Arm 4, who received the IR tablet formulation will be brought back following a 7-day washout period to receive TBI-223 IR Tablets 2000 mg (2 x 1000 mg tablets), under fed conditions. If more than 2 of the 6 subjects drop-out, they will be replaced by healthy volunteers (a minimum of 4 subjects is required to complete the Fed cohort).

Additional cohorts may be enrolled if deemed appropriate (e.g. if bioavailability is lower than expected) by the Sponsor to repeat a dose level, to study other dose levels, change proposed

QMD Ref: Worldwide-TMP-ST-006-4.0 Effective: 12Aug2019	Governing QMD: Worldwide-SOP-ST-001
Confidentiality Statement	

This document is the property of Worldwide Clinical Trials Inc. and may not be duplicated, copied, altered or removed from company without prior approval from Worldwide Quality Assurance or in compliance with Worldwide Standard Operating Procedures.

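### Cohort 9's completion rule counts subjects rather than fed/fasted pairs and conflicts with Appendix 6, and the planned parallel analysis would not show that pairs were lost

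*Protocol*

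**What the plan says.** Protocol Section 3 (Part 2) defines Cohort 9 by return: "The 6 subjects from Cohort 8, Arm 4, who received the IR tablet formulation fasted will return after a 7-day washout" to "receive a single dose of TBI-223 IR Tablets, 2000 mg dose (2 x 1000 mg tablets), under fed conditions". The replacement rule is "If more than 2 subjects of these 6 subjects from Cohort 8 drop-out, they will be replaced by healthy volunteers (a minimum of 4 subjects", the bracket going on to make that number sufficient for completion. The Synopsis, Protocol Section 6.1 and SAP Section 4 repeat it. SAP Section 1 puts the minimum as "a minimum of 4 subjects is required to complete the Fed cohort".

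Appendix 6, to which Section 3 refers for the procedures and analyses of Cohort 9, has a different figure directly after its Cohort 9 paragraph: "A minimum of 6 subjects per treatment arm in Part 2". On added subjects it says only that they will be screened.

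Section 6.4 states: "Please note that Cohort 9 is the same 6 subjects that were in Cohort 8, Arm 4 (IR tablet formulation) under fed conditions". Sections 6.5.1 and 6.7.2 carry the same note. None of the three allows for replacements.

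SAP 6.11 compares IR fed (Cohort 9) with IR fasted (Cohort 8) by an ANOVA for a parallel design, with treatment as the only effect. For the Part 1 food effect (Cohort 5) and the capsule repeat of Cohort 3, the same section uses a crossover model with subject as a random effect. The PK Analysis Set (SAP 6.1.4) does not require both profiles.

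**The concern.** What returning Arm 4 subjects add to the food question is that the same person is measured fasted and fed. A drop-out removes such a person. A new volunteer who takes only the fed dose restores the count but not the pair. As written, the cohort can be called complete when few of its members have both profiles.

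Fed versus fasted absorption is a secondary objective, and the IR tablet is the only tablet given both ways. The sections also give the site two answers about when to replace: with one or two drop-outs, Section 3 asks for nobody, while Appendix 6, read as covering Cohort 9, asks for one or two. It is also unclear whether replacement tops the cohort up to six or only to four.

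**Working it through.** **Inputs from the documents.** Six planned returners; replacement when more than two drop out; minimum four (Section 3); minimum six per treatment arm (Appendix 6); 90% intervals for geometric mean ratios (SAP 3.2). No variance or drop-out rate is given, and the study is stated not to be formally powered.

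**The plan's own figure.** 6 planned − 2 tolerated drop-outs = 4, which reproduces the stated minimum.

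**Pairs.** A replacement has no fasted Arm 4 profile, so pairs = 6 − drop-outs.

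| Drop-outs | Pairs | Section 3 replaces? | New subjects to reach 4 | New subjects to reach 6 |
|---|---|---|---|---|
| 0 | 6 | no | 0 | 0 |
| 1 | 5 | no | 0 | 1 |
| 2 | 4 | no | 0 | 2 |
| 3 | 3 | yes | 1 | 3 |
| 4 | 2 | yes | 2 | 4 |
| 5 | 1 | yes | 3 | 5 |
| 6 | 0 | yes | 4 | 6 |

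The two minima differ in the action required at one and two drop-outs. Neither changes the number of pairs.

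**How often the rule would operate.** The binomial probability of more than 2 drop-outs in 6 is 0.2%, 1.6%, 9.9% and 25.6% at assumed drop-out rates of 5%, 10%, 20% and 30%.

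**Precision of a within-subject analysis.** The half-width on the log scale is t(0.95, n−1) × s_w × √(2/n), with s_w = √ln(1 + CV²). At an assumed within-subject CV of 20%, s_w = 0.198. Around a ratio of 100%:

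- 6 pairs: 2.015 × 0.198 × 0.577 = 0.230, giving 79-126%
- 4 pairs: 2.353 × 0.198 × 0.707 = 0.330, giving 72-139%
- 3 pairs: 2.920 × 0.198 × 0.816 = 0.472, giving 62-160%

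Over assumed CVs of 15% to 30%, six pairs give 84-119% to 71-141%, four give 78-128% to 61-163%, and three give 70-143% to 50-201%.

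**Precision of the planned parallel model.** The half-width is t(0.95, n₁+n₂−2) × s × √(1/n₁ + 1/n₂), where s also contains the between-subject spread. With the same within-subject CV of 20% and an assumed between-subject CV of 30%, s = √(ln 1.04 + ln 1.09) = √(0.0392 + 0.0862) = 0.354.

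- 6 fed v 6 fasted: 1.812 × 0.354 × 0.577 = 0.371, giving 69-145%
- 4 fed v 6 fasted: 1.860 × 0.354 × 0.645 = 0.425, giving 65-153%

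These intervals depend only on the group sizes. Four returners and one returner plus three new volunteers give the same expected width, so the output does not reveal how many pairs lie behind it.

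**The case against.** The strongest answer is that the SAP does not use pairs. Its parallel ANOVA gives a fed/fasted ratio whoever fills the fed group. That stands. A reader might infer that the cohort could be complete with its food question unanswerable; the documents do not support this.

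A reader might also infer that replacement adds between-subject noise to the ratio. It does not. With three of six replaced, three leavers carry weight −1/6 and three new subjects +1/6, so the squared weights sum to 6/36. With three drop-outs and no replacement, three returners carry 1/3 − 1/6 = 1/6 each and three leavers −1/6, again 6/36. Drop-out causes that term and the wider paired intervals above.

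A cohort with no pairs at all needs all six to leave, below 0.1% even at an assumed 30% drop-out rate, so it should carry no weight. Cohort 9 also supplies the IR-fed reference for the SR-fed comparison, where a fed-only replacement is fully usable. SAP 6.11 sets no 80-125% criterion for Part 2, so no stated decision depends on the width.

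On four versus six, Appendix 6 can be read as covering only the four arms of Cohort 8, since Section 3 gives 24 subjects in four arms. That reading is possible, but the bullet speaks of Part 2 as a whole and follows the Cohort 9 paragraph. Finally, that replacements take only the fed dose is an inference from silence. It is the natural one, because Cohort 9 is a single fed dose and no fasted dose is described for anyone joining it.

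**Conclusion.** The point holds as a matter of definition and consistency. The minimum of four is not tied to subjects with both conditions, and whenever replacement operates at most three pairs remain. The minima of four and six, and the notes describing the same six subjects, must be reconciled. The planned analysis would run, but it gives up the benefit of the return design and hides any loss of pairs. With all six returning, the gain from using the pairing is 79-126% against 69-145%, assuming within- and between-subject CVs of 20% and 30%; neither figure comes from the documents.

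For the capsule repeat, Appendix 5 says "Ideally, all 8 subjects who participated in the original cohort will participate in the re-dose cohort". Two of those eight took placebo. They, and any newly screened subjects, have no suspension profile. Nothing more than reporting the number of pairs follows from this.

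**What to change.** 1. In Protocol Sections 3 and 6.1, the Synopsis and SAP Sections 1 and 4, state the Cohort 9 minimum as the number of subjects completing both Arm 4 fasted and Cohort 9 fed. Reconcile it with Appendix 6 and with the notes in Sections 6.4, 6.5.1 and 6.7.2, and say to what number replacement restores the cohort.
2. State that a fed-only replacement contributes to safety and to the SR-fed versus IR-fed comparison, but not to the within-subject food contrast.
3. In SAP 6.11, estimate the IR fed/fasted ratio within subject, with treatment as a fixed effect and subject as an effect, as already planned for Cohort 5. Base it on subjects with both profiles and report the number of pairs. Report it for the capsule/suspension ratio too.

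The cost is protocol and SAP wording, with no added procedures. The downside is that with few pairs the within-subject interval is wide: at three pairs it is 62-160%, against 65-153% for the parallel model with four fed and six fasted under the assumptions above. Fed-only data add little to a within-subject ratio. The parallel estimate could be shown beside the paired one as supportive.
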